SOC	System Organ Class
SOP	Standard Operating Procedure
UP	Unanticipated Problem
US	United States

STATEMENT OF COMPLIANCE

This clinical trial will be carried out in accordance with Good Clinical Practice (GCP) as required by the following:

- United States (US) Code of Federal Regulations (CFR) applicable to clinical studies (45 CFR Part 46, 21 CFR Part 50, 21 CFR Part 56, and 21 CFR Part 812)
- ICH E6

All key personnel (all individuals responsible for the design and conduct of this trial) have completed Human Subjects Protection Training.]

I agree to ensure that all staff members involved in the conduct of this study are informed about their obligations in meeting the above commitments.

Principal Investigator: **Print/Type Name**

Signed: Date: _____

PROTOCOL SUMMARY

Title: Rinovum Subsidiary 2, LLC. Disposable Stress Urinary Incontinence Device Efficacy and Safety Study

Précis: This study is an interventional, single arm, multi-center study. It will be conducted at sites in the northeastern United States. The protocol will be approved by Chesapeake IRB or applicable local IRBs. The sample size will consist of approximately 50 participants. Participants will undergo an initial control period in which preweighed pads will be worn for 7 consecutive days for 12 hours. This will be followed by device usage for 14 consecutive days where participants will wear both device and preweighed pads simultaneously. for 12 hours.

Objectives: The purpose of this study is to evaluate the efficacy and safety of an over-the-counter (OTC) disposable stress urinary incontinence (SUI) pessary device. Specifically, this study will evaluate the effectiveness of the pessary device by assessing reduction in urine leakage in approximately 50 women with Stress Urinary Incontinence (SUI). Efficacy will be assessed by mean pad weight gain per hour, reduction of stress urinary incontinence events per day, and a quality of life questionnaire. The safety of the OTC SUI pessary device will be evaluated by assessing all adverse events, including the results of urinalysis, vaginal swab, and vaginal examination.

Primary Objective: Demonstrate effectiveness of device usage

Important Secondary Objectives: Device reduces episodes of incontinence, improves quality of life, and is safe for over-the-counter (OTC) use.

Endpoints:

Primary Endpoint: Mean pad weight gain reduction per hour is >50% during the last 7 days of the treatment phase as compared to the baseline phase.

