2.2 RATIONALE

This study is an interventional, open label, single-arm, clinical study in which participants will serve as their own controls. This study will enroll participants deemed eligible per the Inclusion/Exclusion Criteria. This study will evaluate the safety and effectiveness of the Rinovum Subsidiary 2 (RS-2) SUI pessary device by assessing reduction in urine leakage in approximately 50 women with SUI. Efficacy will be assessed by reduction in pad weight gain, frequency of stress urinary incontinence events, and a quality of life questionnaire. The study design consists of a control/no treatment period for each subject and a device treatment period for each subject.

The participants in this study will use the pre-weighed pads daily for 12 hours per day to obtain baseline control urine leakage data. This baseline will be for 7 consecutive days. The pads may be changed as necessary during this time. The same participants will use the device, and the same pre-weighed pad method for 14 consecutive days during the treatment period. Participants will be asked to schedule the treatment phase during a time when they will not have an interruption in the treatment phase such as menstrual cycle or travel. Patients will be asked to perform the treatment period within 21 days. In both the non-treatment and treatment phase of the study, the preweighed pads will be collected and weighed for use in calculating pad weight gain (PWG).

Safety analysis will include results of urinalysis, vaginal swab, vaginal examination, and evaluation of adverse events.

Usability of the device will be assessed by the PI at Enrollment where the participant will insert the device while following the Instructions for Use. The PI will examine the device inside the vagina to ensure successful placement and fit.

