4.3 STUDY ENDPOINTS

The primary endpoint is the percentage reduction in mean pad weight gain per hour of >50% during the 14-day treatment phase versus the 7-day baseline phase. The PWG percentage reduction will be calculated by comparing the mean PWG over the 7-day baseline non-treatment phase with the last 7 days of the 14-day treatment phase for each individual participant.

Important secondary endpoints will be measured based on anecdotal evidence or feedback from the subjects. These secondary endpoints are as follows:

- (1) Reduction in mean number of SUI episodes per day from episodes from the 7-day baseline period to the last 7 days of the 14-day device treatment period as measured as reduction (improvement) in stress urinary incontinence episodes. Participants will record SUI episodes in the Study Diary during the baseline (7 days) and treatment (14 days). Negative values are indicative of efficacious outcome.
- (2) Change in Quality of Life as Measured by the ICIQ-LUTSqol Quality of Life Questionnaire.

The Quality of Life Questionnaire to be performed at baseline, before and after treatment phase of the study is based on 20 questions referring to areas which may have been influenced or changed by accidental urine loss and/or prolapse. These questions are assigned a value of, 1 = 'Not at all,' 2= 'Slightly,' 3 = 'Moderately,' or 4 'A lot.' Each area of changed is then assessed on a scale of 1-10 to see how much it bothers them. The Questionnaire is scored by taking the average score of items and then multiplying the average by 25 to put scores on a scale from 0 to 100. A lower score is considered less impact to quality of life and a higher score reflects more impact to quality of life. In the same manner, a reduction in scores from baseline reflects improved quality of life. A reduction on score of ≥ 3.7 is considered the Minimum Clinically Important Difference.

- (3) Evaluation of Adverse Event assessments to determine device is safe for use.

Important Exploratory Endpoints are as follows:

- (1) Participants can successfully use the device in accordance with the given Instructions for Use.
- (2) Participants will find the device comfortable enough to demonstrate compliance with the study procedures during the device treatment phase.

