10 STATISTICAL CONSIDERATIONS

10.1 Populations

Intent to Treat Population (ITT): Any subject enrolled who gets a pre-weighed pad for the control phase. This is expected to be 60-70 subjects.

Modified Intent to Treat Population (mITT): Any subject enrolled who gets through the control phase, is given the device and pads for the treatment period, and who uses the device such that there is at least one data point to analyze - i.e., use of the pad for at least one hour during the last 7 days of the treatment period. A subject who is not in the study at the beginning of the last 7 days of the treatment period is in the ITT population but not the mITT population. **THE mITT IS THE POPULATION THE ANALYSIS WILL BE DONE ON.**

Per Protocol Population (PP): Any subject getting through the entire treatment period and has complete data (i.e., pad weight reduction data for the last 7 days of the treatment period). For example, someone having only data for 6 out of the last 7 days of the treatment period is in the mITT population but not the PP population.

Safety Population (SP): Same as ITT.

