10.4 Statistical Hypotheses and Data Description

1. Type 1 Error and Multiplicity Concerns:

The inferential tests for the one primary and two secondary endpoints were initially conceived to be one-sided using alpha=0.05. Since the sponsor wishes to use the success of all three for labeling and marketing purposes, a Bonferroni adjustment for multiple comparisons will be employed. Thus, statistical significance will be indicated for each endpoint if the p-value is less than 0.0167.

2. Primary Endpoint:

There is one primary endpoint, for efficacy. The objective is to show that reduction in the mean pad weight gain per hour is >50% in the treatment period. Thus, the null hypothesis is that the mean weight gain reduction per hour is <=50%, and the alternative is that it is >50%, from the control period (no device) to the treatment period (women wearing the device). The data values will be computed for each woman as:

[(total weight of all pads worn during the treatment period/hrs. pads are worn during treatment)

minus

(total weight of all pads worn during the control period/ hrs. pads are worn during control)]

The above quantity divided by
(total weight of all pads worn during the control period/ hrs. pads are worn during control)

This resulting quantity is then multiplied by 100.

Ex. Subject's total pad weight for control period is 140 grams. Pads were worn for a total of 100 hours. Weight/hr. is $140/100 = 1.4$ g/hr. Subject's total pad weight for treatment period is 60 grams. Subject wore pads for 100 hours. Pad weight per hour is $60/100 = 0.6$ g/hr. Difference, treatment – control is $0.6 - 1.4 = -0.8$ g/hr. For the percent change, $100 * (-0.8/1.4) = -57.143\%$. Therefore the reduction in pad weight gain is 57.143%.

The null hypothesis will be that the mean reduction in pad weight gain per hour is less than or equal to 50%, with the alternative that it is greater than 50%. If the raw percentage change data appear to be normally distributed, a paired t-test will be used to test the hypothesis. If not, see section 10.6 (2).

The precision method will be utilized to determine success. The precision approach creates a lower bound for a confidence interval that is higher than the reference, in this case 50%. This 50% standard was chosen based on the FDA guidance document.

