Power and sample size calculations determine scenarios of success. When the resulting mean reduction in pad weight gain per hour is quantified, its lower limit of a $(1-0.0167)\%$ confidence level is determined. This value is then compared to parameters determined to be efficacious in the sample size calculations (section 10.3). It is expected that the mean reduction per hour will be >50% such that the lower limit of the confidence interval for that result will be higher than 50% with adequate power to suggest success for the study.

3. Secondary Endpoints:

- a. For the change in SUI episodes endpoint each subject will have a change in the number of episodes per day from the control period to the treatment period. Specifically, the number of episodes will be recorded each day in the diary. For the control phase, there will be (at most) 7 days of data. The mean number of SUI episodes per day will be computed for each subject. The same measures

will occur in the treatment period for the analysis period, the last 7 days. Each subject will again have a mean number of SUI episodes per day. If the pads are not worn for the entire time specified during a day, the fraction of the day the pads are worn will be used in computing the number of days. Therefore, there will be, say, 50 differences comprised of mean number of SUI episodes per day in the treatment period minus mean number of SUI episodes per day for control period. (These numbers will likely be negative.) The mean of these 50 mean differences represents the mean change in the number of SUI episodes per day from the control period to the treatment period. The null hypothesis will then be that the mean change in the number of SUI episodes is 0, and the alternative is that it is less than 0, analyzed using a paired t-test. A p-value of less than 0.0167 indicates success.

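### The plan gives the primary endpoint two treatment windows: the formula and one sentence of 4.3 do not limit it to the last 7 days, as the rest of the plan does

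*Combined protocol and SAP*

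**What the plan says.** Places that point to the last 7 days:

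- The Protocol Summary gives the primary endpoint as "Mean pad weight gain reduction per hour is >50% during the last 7 days of the treatment phase as compared to the baseline phase".
- The second sentence of 4.3 compares the 7-day baseline mean "with the last 7 days of the 14-day treatment phase for each individual participant".
- The PP definition (4.2 and 10.1) requires "pad weight reduction data for the last 7 days of the treatment period". The mITT definition in the same sections requires at least one hour of pad use in those days.

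Places that do not:

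- The first sentence of 4.3 states the endpoint "during the 14-day treatment phase versus the 7-day baseline phase".
- The objective in 10.4(2) is that "reduction in the mean pad weight gain per hour is >50% in the treatment period".
- The treatment term of the formula in 10.4(2) is "total weight of all pads worn during the treatment period/hrs. pads are worn during treatment".
- The log-ratio fallback in 10.6(1)a refers to a post-treatment result and gives no window.

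The plan does not use the term treatment period consistently. Section 2.2 means 14 days by it: "the same pre-weighed pad method for 14 consecutive days during the treatment period". In 10.4(3)a the episode endpoint is first tied explicitly to the last 7 days. The difference is then written as "mean number of SUI episodes per day in the treatment period minus mean number of SUI episodes per day for control period", where the term stands for those 7 days.

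**The concern.** Section 10.4(2) is the only place where each woman's primary value is defined arithmetically, so it is what a programmer would code. Taken literally, it brings week-1 pads and hours into the result, while the Protocol Summary leaves them out. Two analysts could derive different primary values from the same pads, and each could cite the protocol.

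If leakage reduction differs between the two treatment weeks, the mean and its lower confidence limit depend on which reading is taken. The study is open label with a single arm, success turns on that one limit against 50%, and 10.4(1) says the result is meant to support labeling. The window should therefore be fixed in writing before anyone sees pad weights.

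**Working it through.** **1. Do the passages settle the window?** The mITT and PP definitions speak of the last 7 days of the treatment period, so that period is longer than 7 days, and 2.2 makes it 14. All pads worn in that period therefore include week 1. This conflicts with the Protocol Summary and with the second sentence of 4.3, and the two sentences of 4.3 conflict with each other.

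The worked example in 10.4(2) reproduces: 100 × (0.6 − 1.4)/1.4 = −57.143%. It does not settle the window. Its 100 treatment hours exceed 7 × 12 = 84 planned hours, but so do its 100 control hours, so it is only illustrative.

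**2. The plan's own figures.** Table 1 in 10.3 is reproduced by P(χ²₄₉ ≤ 49 × [h√50/(t × SD)]²), with h the half-width and t the one-sided 95% point on 49 df:

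| Half-width | SD | Table 1 | Recomputed |
|---|---|---|---|
| 5 | 16 | 0.999 | 0.999 |
| 5 | 17 | 0.991 | 0.991 |
| 5 | 18 | 0.956 | 0.957 |
| 5 | 19 | 0.869 | 0.872 |
| 5 | 20 | 0.720 | 0.726 |
| 6 | 20 | 0.995 | 0.995 |

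Table 1 depends on the window only through the assumed mean and SD, so it neither supports nor weakens the point.

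**3. What the window can change.** Inputs from the plan: n = 50, a 60% reduction and SDs up to 20% (10.3), and a one-sided test at 0.0167 (10.4). Assumptions that are not in the documents: equal hours in each treatment week, the same SD in both windows, and a week-2 minus week-1 difference of d points.

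With equal hours, R₁₄ = (R_week1 + R_week2)/2 = R_week2 − d/2.

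With t(0.9833, 49 df) = 2.189, the half-width is 2.189 × SD/√50. The 14-day limit reaches 50 when 60 − d/2 − half-width = 50, that is, at d = 2 × (10 − half-width).

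| SD | Half-width | Last-7-day lower limit at observed 60% | d at which 14-day limit is 50% |
|---|---|---|---|
| 16 | 4.95 | 55.0% | 10.1 |
| 18 | 5.57 | 54.4% | 8.9 |
| 20 | 6.19 | 53.8% | 7.6 |

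For example, a week-1 reduction of 50% and a week-2 reduction of 60% give 55% over 14 days. At SD 20 the lower limit is then 55 − 6.19 = 48.8%, against 53.8% for the last 7 days. One reading fails and the other succeeds.

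**4. Chance that the lower limit exceeds 50%.** This uses the noncentral t distribution on 49 df, with noncentrality (true mean − 50)/(SD/√50). The true last-7-day mean is set at 60%. At d = 5 the 14-day mean is 60 − 2.5 = 57.5%.

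| SD | Last 7 days | 14 days, d = 5 |
|---|---|---|
| 16 | 98.6% | 86.7% |
| 18 | 95.6% | 77.4% |
| 20 | 90.8% | 67.8% |

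At d = 0 the two means coincide, and under these assumptions nothing changes.

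**The case against.** The strongest reply is that the plan already shows its intent. The second sentence of 4.3 is a calculation rule and can be read as specifying the looser sentence before it. The mITT rule in 10.1 drops women who are not in the study at the start of the last 7 days, which would make little sense if week 1 counted. Section 10.6 takes the one-day measure of a minimally compliant mITT woman as her analysis value. She would normally have week-1 pads as well, so this fits only a last-7-day window. Section 10.4(3)a names the last 7 days as the analysis period, and 10.2 promises a more detailed SAP.

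This stands as evidence of intent: the last 7 days is the evident reading. It does not remove the conflict. The explicit statement in 10.4(3)a concerns the episode endpoint, with no matching clause for the primary endpoint, and a later SAP cannot follow both sentences of 4.3.

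The objections to the size of the effect are also partly right:

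- d = 5 has no source, and a negative d would favor the 14-day reading.
- Equal SD is the least favorable case for 14 days when the two weeks have equal SDs. With between-week correlation r, the 14-day SD is SD × √((1 + r)/2). At SD 20 and d = 5 the chance of success is then 0.81, 0.75 or 0.70 for r = 0.5, 0.7 or 0.9, against 0.68 at r = 1.
- At the one-sided 0.05 used in 10.3, the thresholds for d rise to 12.4, 11.5 and 10.5. The level in 10.4 for declaring significance is 0.0167, so the figures above use that.

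**Conclusion.** The concern holds and should be fixed before analysis. The direct contradiction is within 4.3. Section 10.4(2) leaves the window out of the operative formula, and 10.6(1)a carries the omission into the fallback analysis. The intended window can be inferred, so the design is not at fault, but the stated computation of the deciding endpoint is wrong as written.

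The practical size is unknown, because nothing in the documents says how far the two treatment weeks differ. Under equal hours, equal SD and one-sided 0.0167, a week difference of about 8 to 10 points is enough to bring the 14-day limit down to 50% when the last 7 days show 60%. A smaller correlation between weeks or a looser alpha raises that threshold. These figures show that the window can decide the result; they do not predict that it will.

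**What to change.** - **4.3, first sentence:** replace the 14-day phase with the last 7 days of the 14-day treatment phase.
- **10.4(2):** limit the treatment term to those 7 days, for both pads and hours, and bring the objective sentence into line.
- **10.6(1)a:** define the post-treatment result as the same last-7-day hourly rate.
- **Editorial, at the same time:** in the formula and worked example, write weight gain (used minus pre-use weight) where only weight is stated.

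The cost is wording in three sections, settled before pad data are seen. No new data are needed, and the sample size does not change.

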Total N: Obtain informed consent. Screen potential participants by inclusion and exclusion criteria; obtain and document medical history. Confirm that participant symptoms indicate SUI diagnosis. Perform the urine pregnancy test (if applicable), urinalysis, vaginal examination and symptom evaluation to ensure participant has no active urinary or vaginal infection requiring treatment. A vaginal swab will be performed to establish baseline vaginal microflora. Perform usability and fit assessment test.

NOTE: Results of the SUI diagnosis assessment and fit assessment may deem participant ineligible for enrollment due to urge incontinence or mixed (stress and urge) incontinence diagnosis or poor /improper fit. To simulate OTC use, participants will be asked to perform self-selection and assess fit based on the product labeling prior to confirmation by the PI.

Enrollment/Visit 1 Time Point

Total N: Complete a questionnaire by the physician. Participant will also complete a baseline Quality of Life Questionnaire.

Participant will receive 14 preweighed pads to take home. Participant will perform control phase of study wearing pads for 12 hours/day for 7 consecutive days. Pads will be returned by participant for weighing and data collection.

NOTE: Results of the laboratory tests from the screening visit (pregnancy test, vaginal examination and urinalysis test) may deem a participant ineligible for enrollment due to positive pregnancy result, positive vaginal infection requiring treatment, or positive urinary infection requiring treatment, respectively.

Visit 2 Time Point

Total N: Urine pregnancy test, if applicable, to rule out pregnancy, vaginal examination, and symptom evaluation will be repeated to rule out any potential infection requiring treatment. Vaginal swab will also be repeated to evaluate changes in vaginal microflora. Quality of Life questionnaire will be repeated. Participants will be given 20 study devices and 28 preweighed pads to perform the treatment phase of the study. Participants will wear 14 devices and 14 pads simultaneously for 14 consecutive days. Pads will be returned by participant for weighing and data collection, and participants will record information regarding activity level and quality of life.

Visit 3 Time Point

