- Administer the Treatment Study Diary
- Physician will administer 20 devices and 28 preweighed pads to wear both device and pad simultaneously for 14 consecutive days.
- Record any adverse events

NOTE: to minimize time between pad wearing and pad weighing, participants will be mailing back all worn pads immediately upon completion of every 7-day wear to the site. The site will record the pad weights in the Pad Weigh Log form. If the participant returns for Visit #3 within 2 days of completing the 14-day wear, they may bring the remaining 7 worn pads to the visit in lieu of mailing in pads at the physician's discretion.

Visit #3 schedule shall consist of the following:

- Update Medical History, if applicable
- Perform a urinalysis and vaginal microflora swab
- Assess for any active vaginal infection
- Collect and review the Treatment Study Diary
- Collect and weigh any remaining worn pads, if applicable
- Complete the Final Questionnaire
- Complete the post-treatment Quality of Life Survey
- Record any adverse events

Procedures	Screening	Enrollment/ Baseline (Visit 1) ¹	Follow-Up (Visit 2)	Follow-Up (Visit 3)
Informed consent	X			
Demographics	X			
Medical history	X	X	X	X
Physical exam	X			X
Vital signs	X	X	X	X
Height	X			X
Weight	X			X
Human Factors and Fit Assessment	X			
Urine Pregnancy Test (if applicable)	X		X	
Urinalysis	X			X
Administer Investigational Product			X	
Adverse event evaluation		X	X	X
Vaginal swab	X		X	X
Questionnaire	X	X	X	X
Quality of Life Survey		X	X	X

(1) Enrollment must be take place within 1 week of screening. Otherwise, screening procedures must be repeated prior to enrollment

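### The primary-endpoint formula in Section 10.4(2) is written in total pad weight, not pad weight gain; applied literally, dry pad mass dilutes a real reduction and could fail an effective device

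*Combined protocol and SAP*

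**What the plan says.** Section 10.4(2) gives the only operational definition of the primary value. Its treatment term is "total weight of all pads worn during the treatment period/hrs. pads are worn during treatment". Its control term, which is also the divisor, is "total weight of all pads worn during the control period/ hrs. pads are worn during control". The worked example uses the same language ("Subject's total pad weight for control period is 140 grams"; "Subject's total pad weight for treatment period is 60 grams"), yet its last line calls the result a reduction in pad weight gain.

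Everything around the formula refers to gain: the objective and hypotheses in Section 10.4(2), the primary endpoint in the Protocol Summary, Section 4.3, and Section 2.1 on why pads are weighed. Section 2.2 says "the preweighed pads will be collected and weighed for use in calculating pad weight gain (PWG".

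Section 7.3 has worn pads returned in preweighed ziplock bags and has the site log pad weights. It does not say that a net weight is derived.

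On pad numbers, Section 7.3 supplies 14 pads for the 7 control days and 28 for the 14 treatment days, and Sections 2.1 and 2.2 allow changes during the day. The Schematic of Study Design says "Participants will wear 14 devices and 14 pads simultaneously for 14 consecutive days". The Visit 2 note in Section 7.3 says of participants that "they may bring the remaining 7 worn pads to the visit".

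**The concern.** Total weight of worn pads is dry pad mass plus leaked urine, and only the urine is the endpoint. Preweighing exists so that the dry part can be removed, and the formula omits that step. The bags raise the same issue if pads are weighed inside them.

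A programmer working from the one explicit formula would compute a different variable from the one in the hypotheses. The log-ratio fallback in Section 10.6 and the site-adjusted model in Section 10.7 would inherit it. This is the sole primary endpoint and is intended to support labeling. The 50% bar and the 60% planning value in Section 10.3 have their meaning only for net gain.

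**Working it through.** **Inputs from the plan.** Example: 140 g over 100 h and 60 g over 100 h (Section 10.4(2)). Success bar: 50%. Planning reduction 60%, largest planning SD 20%, n = 50 (Section 10.3). One-sided significance level 0.0167 (Section 10.4(1)).

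**Assumptions, not in the documents.** Dry mass d per pad, shown over a range; control-week gain G = 140 g; 14 or 7 pads per week; equal hours in the two weeks. Any bag mass left in would add to d.

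**1. The plan's own figure.** 100 × (0.6 − 1.4)/1.4 = −57.143%. This reproduces. The arithmetic is right; whether the result is a reduction in gain depends on 140 g and 60 g being gains.

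**2. Equal pad counts.** Let D be the total dry mass in each week (pads × d) and r the true reduction in gain. The literal formula returns

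R = 1 − [D + G(1 − r)]/(D + G) = r × G/(G + D).

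With r = 60% and G = 140 g, so that rG = 84 g:

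| d per pad | 14 pads each week | 7 pads each week |
|---|---|---|
| 1 g | 84/154 = 54.5% | 84/147 = 57.1% |
| 2 g | 84/168 = 50.0% | 84/154 = 54.5% |
| 5 g | 84/210 = 40.0% | 84/175 = 48.0% |
| 10 g | 84/280 = 30.0% | 84/210 = 40.0% |

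**3. Where a true 60% drops to the bar.** 0.60 × G/(G + D) > 0.50 requires D < 0.20 × G. For G = 140 g that is 28 g of dry mass in total: 2 g per pad with 14 pads, or 4 g with 7.

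**4. Power.** One-sample t-test against 50%, n = 50, one-sided 0.0167. With net weights, a mean of 60% and SD of 20% give power 0.91. With the literal formula and 14 pads in each week, mean and SD both shrink by G/(G + D), taking the dry share as the same for every woman. Power becomes 0.34 at 1 g, 0.017 at 2 g (the mean then sits exactly on the null) and about 0 at 5 g.

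**5. Unequal pad counts.** In general R = w × (reduction in pads per hour) + (1 − w) × r, where w is the dry share of total control weight. Take 14 pads falling to 7, equal hours and no change in leakage: R = 7d/(14d + 140).

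- d = 5 g: 35/210 = 16.7%
- d = 10 g: 70/280 = 25.0%
- d = 20 g: 140/420 = 33.3%

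This approaches 50% as dry mass dominates but cannot exceed it.

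A partial effect can nevertheless be inflated, because light leakers have the larger dry share. An illustration with 5 g pads, 14 against 7:

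- Gain 280 g, true reduction 80%: 1 − (35 + 56)/(70 + 280) = 74%.
- Gain 35 g, true reduction 10%: 1 − (35 + 31.5)/(70 + 35) = 36.7%.

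The true mean is (80 + 10)/2 = 45%. The formula's mean is (74 + 36.7)/2 = 55.3%.

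**The case against.** The strongest reply is that nobody would run the formula this way. Gain is named in the objective, the hypotheses and the example's conclusion within the same section, and in Sections 2.1, 2.2 and 4.3. Pads and bags are both preweighed. The example itself fits gains better: a gross 60 g is impossible with 14 pads of 5 g or with 7 pads of 10 g, since the dry mass alone would be 70 g. Section 10.2 promises a more detailed SAP, and the Pad Weight Log form, which is not in the documents, may already carry a net weight. All of this stands as evidence of intent. A reader might infer that the sponsor chose gross weight as the endpoint; the documents do not support that. But none of it supplies the missing step, and the one explicit rule says something else.

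A reader might also infer that pads fall from 14 in the control week to 7 in the last treatment week. That compares pads supplied in control with pads worn in treatment. Like for like, supply is two a day in both phases (14/7 and 28/14), and the number actually worn in control is not stated. A difference in pads per hour is possible but not established.

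**Conclusion.** The formula and its example are wrong as written and contradict the endpoint they implement. The intended variable is clear, so this is a defect in the operational definition, not a wrong choice of endpoint.

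If the wording is followed, the main consequence is a false failure. How large the dilution is depends on dry pad mass and control gain, neither of which the documents give. The general result does not need them: with equal pad counts and hours, a true 60% reduction clears 50% only when dry mass is under 20% of control gain.

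The tempting stronger reading is that a device with no effect could pass on pad count alone. A fall from 14 to 7 pads at equal hours with unchanged leakage cannot do it. Pads per hour would have to fall by more than half; for example, 7 pads over 100 h against 14 over 84 h is a 58% fall. What remains in that direction is inflation of a partial effect, conditional on a difference in pad use that the documents do not show.

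**What to change.** In all three places in Section 10.4(2), replace the total-weight term with: the sum over returned pads of (worn weight minus the pre-use weight of that pad and its bags), divided by hours worn. State that the control term covers the 7 baseline days and the treatment term the last 7 treatment days, as in the calculation sentence of Section 4.3; the formula now says only treatment period. Relabel the example's 140 g and 60 g as total pad weight gain; its 57.143% is unchanged. Confirm that the Pad Weight Log records pre-use weight, worn weight and gain for each pad.

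With net weights, dry mass drops out and a true 60% is measured as 60% whatever the pad count. The cost is wording, since pads and bags are already preweighed, plus a derived gain column if the log lacks one.
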